6.4.2. Additional considerations

The percentage of doses with unsolicited AEs occurring within 31-day (Day 1-Day 31) follow-up period after any dose with its exact 95% CI will be tabulated by preferred term. Similar tabulation will be done for unsolicited AEs rated as grade 3, for unsolicited AEs with causal relationship to vaccination, for unsolicited AE resulting in medically attended visit.

Safety analysis will be done per administered dose. Subjects who missed reporting symptoms (solicited/unsolicited or concomitant medications) will be treated as subjects without symptoms (solicited/unsolicited or concomitant medications, respectively). A sensitivity analysis will be performed on documented doses i.e. accounting only for doses where solicited symptoms are indicated as being absent/present in case more than 5% of the doses are not documented.

Because the summary of subjects withdrawn from the study mentioned in Section 6.1.1 includes SAE and AE as separate reason categories and such SAE/AE are described by narrative in the study report, the summary by preferred term planned for AEs or SAEs leading to drop out in Section 6.4.1.1 will not be generated.

Summary of temperature will be provided by 0.5° increment (i.e. $\geq 38.0^{\circ}\text{C}$, >38.5 ; > 39 , > 39.5 , > 40). Fever, defined as a body temperature of $\geq 38^{\circ}\text{C}$ irrespective of route of measurement, will be integrated to the summaries as a general symptom.

CONFIDENTIAL

116566 (ROTA-083)
Statistical Analysis Plan Amendment 2

7. ANALYSIS INTERPRETATION

Except for analyses addressing criteria specified in the primary objective, all the analyses will be descriptive/exploratory in nature. The use of these descriptive/exploratory analyses should be limited to support the confirmatory analyses or to generate hypothesis.

8. CONDUCT OF ANALYSES

8.1. Sequence of analyses

Description	Analysis ID	Disclosure Purpose (CTRS=public posting, SR=study report, internal)	Dry run review needed (Y/N)	Study Headline Summary (SHS) requiring expedited communication to upper management (Yes/No)	Reference for TFL
Final	E1_01	SR	Yes	Yes	All tables from TFL TOC

8.2. Statistical considerations for interim analyses

Not applicable.

9. CHANGES FROM PLANNED ANALYSES

Not applicable.

10. LIST OF FINAL REPORT TABLES, LISTINGS AND FIGURES (TFL)

The TFL Table Of Content (TOC) is as separate document. It provides the list of tables/listings and figures needed for the study report, and It also identifies the tables eligible for each analysis and their role (synopsis, in-text, post-text, SHS, CTRS).

The following group names will be used in the TFLs, to be in line with the T-domains:

Group order in tables	Group label in tables	Group definition for footnote
1	HRV Liq	HRV liquid vaccine
2	HRV Lyo	HRV lyophilised vaccine

CONFIDENTIAL116566 (ROTA-083)
Statistical Analysis Plan Amendment 2**11. ANNEX 1 STANDARD DATA DERIVATION RULE AND STATISTICAL METHODS****11.1. Statistical Method References**

The exact two-sided 95% CIs for a proportion within a group will be the Clopper-Pearson exact CI [Clopper CJ, Pearson ES. The use of confidence or fiducial limits illustrated in the case of binomial. *Biometrika*. [1934;26:404-413].

The standardised asymptotic two-sided 95% CI for the group difference in proportions is based on the method described in the following paper: Robert G. Newcombe, interval estimation for the difference between independent proportions: comparison of eleven methods, *Statist Med*. 1998; 17, 873-890]. The standardised asymptotic method used is the method six.

The GMC group ratio will be obtained using an ANCOVA model on the logarithm-transformed concentrations. This model will include the vaccine group and the logarithm of the baseline concentration as covariables. The ANCOVA model will include the vaccine group. The GMC ratio and their 95% CI will be derived by exponential transformation of the corresponding group contrast in the model.

11.2. Standard data derivation**11.2.1. Date derivation**

- SAS date derived from a character date: in case day is missing, 15 is used. In case day & month are missing, 30June is used.
- Onset day for an event (AE, medication, vaccination, ...): the onset day is the number of days between the last study vaccination & the onset/start date of the event. This is 1 for an event starting on the same day as a vaccination. See SAS date derived in case the start date of the event is incomplete.
- Duration: Duration of an event is expressed in days. It is the number of days between the start & the stop dates + 1. Therefore duration is 1 day for an event starting & ending on the same day.

11.2.2. Dose number

- The study dose number is defined in reference to the number of study visits at which vaccination occurred. More specifically dose 1 refers to all vaccines administered at the first vaccination visit while dose 2 corresponds to all vaccinations administered at the second vaccination visit even if this is the first time a product is administered to the subject.

CONFIDENTIAL116566 (ROTA-083)
Statistical Analysis Plan Amendment 2

- Relative dose: the relative dose for an event (AE, medication, vaccination) is the most recent study dose given before an event. In case the event takes place on the day a study dose is given, the related dose will be that of the study dose, even if the event actually took place before vaccination. For instance, if an adverse event begins on the day of the study vaccination but prior to administration of the vaccine, it will be assigned to this dose. In case a study dose is not administered and an event occurs after the subsequent study dose (e.g. 3rd study dose), the relative dose of the event will be study dose associated to the subsequent study dose (e.g. dose 3).
- The number of doses for a product is the number of time the product was administered to a subject.
- The incidence per dose is the number of vaccination visits at which an event was reported among all vaccination visits.

11.2.3. Demography

- Age: Age at the reference activity, computed as the number of complete weeks between the date of birth and the reference activity.

11.2.4. Immunogenicity

- For a given subject and given immunogenicity measurement, missing or non-evaluable measurements will not be replaced.

The GMCs calculations are performed by taking the anti-log of the mean of the log concentration transformations. Antibody concentrations below the cut-off of the assay will be given an arbitrary value of half the cut-off of the assay for the purpose of GMC calculation.

- In general, the assay cut-off is the value under which there is no quantifiable result available. For an assay with a specific ‘assay cut_off’, numerical immuno result is derived from a character field (rawres):
 - If rawres is ‘NEG’ or ‘-’ or ‘(-)’, numeric result= assay cut_off/2,
 - if rawres is ‘POS’ or ‘+’ or ‘(+)’, numeric result = assay cut_off,
 - if rawres is ‘< value’ and value<=assay cut_off, numeric result =assay cut_off/2,
 - if rawres is ‘< value’ and value>assay cut_off, numeric result =value,
 - if rawres is ‘> value’ and value<assay cut_off, numeric result =assay cut_off/2,
 - if rawres is ‘> value’ and value>=assay cut_off, numeric result =value,
 - if rawres is ‘<= value’ or ‘>= value’ and value<assay cut_off, numeric result =assay cut_off/2,
 - if rawres is ‘<= value’ or ‘>= value’ and value>=assay cut_off, numeric result =value,
 - if rawres is a value < assay cut_off, numeric result = assay cut_off/2,

CONFIDENTIAL116566 (ROTA-083)
Statistical Analysis Plan Amendment 2

- if rawres is a value \geq assay cut_off, numeric result = rawres,
- else numeric result is left blank.

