3.2. Secondary objectives

- To assess the immunogenicity of the HRV liquid vaccine and HRV lyophilized vaccine, in terms of seroconversion* rates, one month post dose 2 of HRV vaccine.
 - * *Seroconversion is defined as:*
 - *for subjects with a pre-vaccination anti-RV IgA antibody concentration <20 U/mL, seroconversion is achieved when the post-vaccination concentration is ≥20 U/mL.*
 - *for subjects with a pre-vaccination anti-RV IgA antibody concentration ≥20 U/mL, seroconversion is achieved when the post-vaccination concentration is ≥2 times the pre-vaccination concentration.*
- To assess the reactogenicity of the HRV liquid vaccine and the HRV lyophilized vaccine in terms of solicited adverse events (AEs), during the 8-day (Day 1–Day 8) follow-up period after each vaccination.
- To assess the safety of the HRV liquid vaccine and the HRV lyophilized vaccine in terms of unsolicited AEs, during the 31-day (Day 1–Day 31) follow-up period after each vaccination and serious adverse events (SAEs), during the entire study period.

Refer to Section 4.2 for the definition of the secondary endpoints.

4. ENDPOINTS**4.1. Primary Endpoint**

- Anti-RV IgA antibody concentrations
 - Serum anti-RV IgA antibody concentrations, expressed as GMCs, one month post dose 2 of HRV vaccine.

CONFIDENTIAL116566 (ROTA-083)
Statistical Analysis Plan Amendment 2**4.2. Secondary Endpoints**

- Anti-RV IgA antibody concentrations
 - Anti-RV IgA antibody seroconversion rate, one month post dose 2 of HRV vaccine.
- Solicited general symptoms
 - Occurrence of each type of solicited general symptom within the 8-day (Day1-Day 8) solicited follow-up period, after each dose of HRV vaccine.
- Unsolicited adverse events
 - Occurrence of unsolicited AEs within 31 days (Day 1-Day 31) after any dose of HRV vaccine according to Medical Dictionary for Regulatory Activities (MedDRA) classification.
- Serious adverse events
 - Occurrence of SAEs from dose 1 of HRV vaccine up to study end.

5. ANALYSIS SETS**5.1. Definition****5.1.1. Exposed Set**

The Exposed Set (ES) will include all subjects with at least one study vaccine administration documented.

- A safety analysis based on the ES will include all vaccinated subjects.
- An immunogenicity analysis based on the ES will include all vaccinated subjects for whom immunogenicity data is available.

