6.3.1.2.1. Definitions related with between groups assessment

- A seronegative subject is a subject whose anti-RV IgA antibody concentration is below the clinical meaningful threshold of <20 U/ml*.
- A seropositive subject is a subject whose anti-RV IgA antibody concentration is greater than or equal to the clinical meaningful threshold of 20 U/ml.
- Seroconversion is defined as:
 - *for subjects with a pre-vaccination anti-RV IgA antibody concentration <20 U/mL, seroconversion is achieved when the post-vaccination concentration is ≥ 20 U/mL.*
 - *for subjects with a pre-vaccination anti-RV IgA antibody concentration ≥ 20 U/mL, seroconversion is achieved when the post-vaccination concentration is ≥ 2 times the pre-vaccination concentration.*
- The GMCs calculations are performed by taking the anti-log of the mean of the log concentrations transformations. Antibody concentrations below the technical cut-off (<13 U/ml*) of the assay will be given an arbitrary value of half the cut-off for the purpose of GMC calculation.

CONFIDENTIAL116566 (ROTA-083)
Statistical Analysis Plan Amendment 2

* Note: 20 U/ml corresponds to the clinical meaningful threshold to define seroconversion rate, while 13 U/ml corresponds to technical cut-off of revalidated laboratory assay.

An immunogenicity analysis based on the ES will include all vaccinated subjects for whom immunogenicity data is available. For the immunogenicity measurement, missing or non-evaluable measurements will not be replaced.

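### SAP 11.2.4 codes a result reported as `<20` as 20 U/mL, so an infant known to be below the threshold is classed as seropositive

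*SAP*

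**What the plan says.** SAP Amendment 2, section 11.2.4, derives a numeric concentration from the raw character field. Two lines deal with results reported as below a value:

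- bound at or below the cut-off: "value<=assay cut_off, numeric result =assay cut_off/2";
- bound above the cut-off: "value>assay cut_off, numeric result =value".

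Section 6.3.1.2.1 fixes the cut-off for this assay: "13 U/ml corresponds to technical cut-off of revalidated laboratory assay". Section 11.2.4 explains what a cut-off means: "the assay cut-off is the value under which there is no quantifiable result available".

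Serostatus uses a second, higher threshold. Section 6.3.1.2.1 calls a subject seropositive when the concentration is "greater than or equal to the clinical meaningful threshold of 20 U/ml". Under section 3.2, seroconversion for a baseline below 20 U/mL requires that "the post-vaccination concentration is ≥20 U/mL". For a baseline of 20 U/mL or more it requires that "the post-vaccination concentration is ≥2 times the pre-vaccination concentration". Section 6.3.2 adds analyses restricted to infants in the per-protocol set (PPS) with baseline below 20 U/mL.

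Neither document says that a result reported only as a bound is classified in any way other than through its derived number.

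**The concern.** A result reported as `<20` carries one certain fact: the concentration is below 20 U/mL. The rule replaces it with the one value at the edge of that range which the report excludes, and the inclusive threshold then turns it into a positive. The rule also jumps. `<13` becomes 6.5 but `<14` becomes 14, and `<20` is treated exactly like `<=20`, although only the latter allows a value of 20.

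The problem arises because this study has a technical cut-off (13) below its clinical threshold (20). If the two coincided at 20, `<20` would become 20/2 = 10 and be classed correctly.

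At stake are seropositivity at each visit, the secondary seroconversion endpoint, and membership of the subset that the Indian regulator requested. The Visit 3 outcome and the baseline covariate in the primary ANCOVA also receive the upper bound, but that matters much less.

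**Working it through.** The plan gives no figure for this point, so the check applies the stated rules to possible results and then sizes one misclassified infant.

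**Inputs.** Cut-off 13 U/mL and threshold 20 U/mL, inclusive (SAP 6.3.1.2.1). Two-part seroconversion rule (SAP 3.2). 225 infants per arm, SD 0.790 on the log10 scale, and non-evaluable shares of 13% and 35% (Protocol 10.3). Margin 0.5 (SAP 3.1). Baseline seropositivity 47.5% in the first 141 infants (Protocol, rationale for Amendment 4).

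**Arm sizes.** 225 × 0.65 = 146.25, so 146; 225 × 0.87 = 195.75, so 195. As a check on the inputs, power at 35% non-evaluable is Φ(0.301 / (0.790 × √(2/146.25)) − 1.96) = 90.3% (90.1% with the t distribution), against the stated 90%. The present point leaves power unchanged.

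**Step 1: reported result to number to serostatus.**

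| Reported | Number | Class under the SAP | Does the bound agree? |
|---|---|---|---|
| `<13` | 6.5 | seronegative | yes |
| `<15` | 15 | seronegative | yes |
| `<19.9` | 19.9 | seronegative | yes |
| `<20` | 20 | seropositive | no |
| `<26` | 26 | seropositive | undetermined |

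Among bounds up to 20, only `<20` itself is misclassified.

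**Step 2: seroconversion.**

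| Baseline | Visit 3 | SAP result | Correct? |
|---|---|---|---|
| `<13` (6.5) or 15 | `<20` (20) | seroconverted | no, known to be below 20 |
| 20, 30 or 40 | `<20` (20) | not seroconverted | yes |
| `<20` (20) | 20 or 30 | not seroconverted, needs 2 × 20 = 40 | no, the first part of the rule should apply and is met |
| 20 | `<40` (40) | seroconverted, 40 ≥ 2 × 20 | no, known to be below 40 |

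An infant whose baseline is reported as `<20` also leaves the SAP 6.3.2 subset, because 20 is not below 20.

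**Step 3: size for seroconversion.** One false seroconverter adds 1/146 = 0.68 percentage points to that arm's rate, or 1/195 = 0.51. The documents give no count. Assuming 1 to 10 in one arm of 146, the rate is 0.7 to 6.8 points too high. If the 47.5% carries over, the subset holds about 195 × 0.525 = 102 infants per arm, and one false seroconverter there adds 1/102 = 0.98 points.

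**Step 4: size for the GMC.** Take the same 1 to 10 results in one arm of 146, without baseline adjustment.

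- If each infant is truly below 13, the SAP's own value would be 6.5. The GMC is inflated by (20/6.5)^(1/146) = 1.008 to (20/6.5)^(10/146) = 1.080.
- If each lies between 13 and 20, the most it can be inflated by is (20/13)^(1/146) = 1.003 to (20/13)^(10/146) = 1.030.

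Per sample, these shifts are log10(20/6.5) = 0.49 and log10(20/13) = 0.19.

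**The case against.** The best defence is that the input may never arise. Section 11.2.4 is a generic list, with lines for qualitative results that an ELISA reported in U/mL has little use for. The assay quantifies from 13 U/mL, so a concentration between 13 and 20 would normally be reported as a number, and the usual censored report would be `<13`. A higher starting dilution for a small sample could produce `<20`, but that is an assumption. Protocol 5.6.9.1 gives about 0.7 mL of serum, and Appendix A says nothing on starting dilution. This stands, and it limits how much the point matters. It does not make the rule right, because the SAP expressly covers such an input and misclassifies it.

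A reader might infer that the rule always pushes status the wrong way, or always inflates seroconversion. The documents do not support either reading. `<15` stays seronegative, a Visit 3 `<20` with baseline of 20 or more is correctly not a seroconversion, and a baseline `<20` makes seroconversion harder.

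A reader might also infer a threat to the non-inferiority conclusion. The laboratory is blinded to treatment (Protocol 5.3) and the same coding applies in both arms, so most of any effect should cancel in the ratio. Seroconversion itself is descriptive (Protocol 10.9, SAP 7).

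Recoding the numbers or leaving them blank as a remedy would have its own cost. The PPS needs both results (SAP 5.1.2), and an unknown baseline status or a missing Visit 3 result triggers elimination codes 2020 or 2100 (SAP 5.2.2.1).

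**Conclusion.** The rule is wrong as written, in a narrow way. A `<20` report is classed as seropositive at either visit. It yields a false seroconversion only at Visit 3 when the numeric baseline is below 20. At baseline it raises the bar for seroconversion and removes the infant from the SAP 6.3.2 subset. In the second part of the rule, only a Visit 3 upper bound equal to exactly twice the baseline is miscounted.

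The size depends on an unknown count, possibly zero. The 0.7 to 6.8 point range is an illustration, not a forecast, and the 10-in-one-arm end is extreme given a blinded laboratory. On that footing the effect on the primary GMC ratio is expected to be negligible. The point is a minor correction that is worth making before the data are analysed, because it removes a later judgement about individual infants in an open-label study.

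**What to change.** Add to SAP 11.2.4 that classification follows the reported bound:

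- a result below a value, with that value at or under 20, is classed as below 20 U/mL for seropositivity, seroconversion and the SAP 6.3.2 subset;
- when baseline is 20 U/mL or more, a Visit 3 result below a value, with that value at or under twice the baseline, is not a seroconversion.

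Keep the existing numeric substitution for the GMC, so that no result becomes missing and no infant leaves the PPS. The small upward shift in the GMC then remains, knowingly.

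List every `< value` result with a bound above 13, and every `> value` or `>= value` result with a bound below 13. The last two are set to 6.5, which can lie under the reported bound (`>10` becomes 6.5). The listing also shows cases such as `<26`, whose status the bound cannot settle and which stay on the numeric rule.

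The cost is one line of derivation code and one listing. If no such results exist, nothing else changes.

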11.2.5. Safety

- For analysis of solicited, unsolicited adverse events (such as serious adverse events or adverse events by primary MedDRA term) and for the analysis of concomitant medications, all vaccinated subjects will be considered. Subjects who did not report the event or the concomitant medication will be considered as subjects without the event or the concomitant medication respectively.
- In case there will be more than 5% of subjects without documented dose for solicited symptoms (i.e., symptom screen not completed), sensitivity analysis will include only vaccinated subjects for doses with documented safety data (i.e., symptom screen completed).
- The following rules will be used for the analysis of solicited symptoms:
 - Subject who didn't document the presence or absence of a solicited symptom after one dose will be considered not having that symptom after that dose in the analysis done on "administrated dose".
 - Subjects who documented the absence of a solicited symptom after one dose will be considered not having that symptom after that dose.
 - Subjects who documented the presence of a solicited symptom and fully or partially recorded daily measurement over the solicited period will be included in the summaries at that dose and classified according to their maximum observed daily recording over the solicited period.
 - Subjects who documented the presence of a solicited symptom after one dose without having recorded any daily measurement will be considered as having that symptom after that dose).
- Intensity of the following solicited AEs will be assessed as described in [Table 5](#) and [Table 6](#).

CONFIDENTIAL116566 (ROTA-083)
Statistical Analysis Plan Amendment 2**Table 5 Intensity scales to be used by the parent(s)/LAR(s) for solicited symptoms during the solicited follow-up period**

Adverse Event	Intensity grade	Parameter
Fever*		Record temperature in °C/°F using any age-appropriate route.
Irritability/Fussiness	0	Behavior as usual
	1	Crying more than usual/no effect on normal activity
	2	Crying more than usual/interferes with normal activity
	3	Crying that cannot be comforted/prevents normal activity
Diarrhea§		Record the number of looser than normal stools/day
Vomiting§		Record the number of vomiting episodes/day
Loss of appetite	0	Appetite as usual
	1	Eating less than usual/no effect on normal activity
	2	Eating less than usual/interferes with normal activity
	3	Not eating at all
Cough/runny nose	0	Normal
	1	Cough/runny nose which is easily tolerated
	2	Cough/runny nose which interferes with daily activity
	3	Cough/runny nose which prevents daily activity

*Fever is defined as temperature $\geq 38.0^{\circ}\text{C}/100.4^{\circ}\text{F}$. The preferred location for measuring temperature in this study will be the oral cavity, the axilla and the rectum.

§ Diarrhea is defined as passage of three or more looser than normal stools within a day.

§ Vomiting is defined as one or more episodes of forceful emptying of partially digested stomach contents ≥ 1 hour after feeding within a day.

Table 6 Intensity scales for diarrhea, vomiting and fever occurring during the solicited period

Adverse Event	Intensity grade	Parameter
Diarrhea §	0	Normal (0-2 looser than normal stools/day)
	1	3 looser than normal stools/day
	2	4-5 looser than normal stools/day
	3	≥ 6 looser than normal stools/day
Vomiting §	0	Normal (no emesis)
	1	1 episode of vomiting/day
	2	2 episodes of vomiting/day
	3	≥ 3 episodes of vomiting/day
Fever	0	temperature $< 38.0^{\circ}\text{C}/100.4^{\circ}\text{F}$
	1	temperature $\geq 38.0^{\circ}\text{C}/100.4^{\circ}\text{F} - \leq 38.5^{\circ}\text{C}/101.3^{\circ}\text{F}$
	2	temperature $> 38.5^{\circ}\text{C}/101.3^{\circ}\text{F} - \leq 39.5^{\circ}\text{C}/103.1^{\circ}\text{F}$
	3	temperature $> 39.5^{\circ}\text{C}/103.1^{\circ}\text{F}$

§ Diarrhea is defined as passage of three or more looser than normal stools within a day.

§ Vomiting is defined as one or more episodes of forceful emptying of partially digested stomach contents ≥ 1 hour after feeding within a day.

CONFIDENTIAL116566 (ROTA-083)
Statistical Analysis Plan Amendment 2

- Note that for all tables described in this section, the way the percentage of subjects will be derived will depend on the event analysed (see table below for details). As a result, the N value will differ from one table to another.

Event	N used for deriving % per subject for Vaccination phase	N used for deriving % per dose for Vaccination phase
Concomitant vaccination	All subjects with study vaccine administered	All study visits with study vaccine administered
Solicited general symptom	Primary analysis: all subjects with study vaccine administered Sensitivity analysis as applicable, all subjects with at least one solicited general symptom documented as either present or absent (i.e., symptom screen completed)	Primary analysis: all study visits with study vaccine administered Sensitivity analysis: all study visits with study vaccine administered and with at least one solicited general symptom documented as either present or absent (i.e., symptom screen completed)
Unsolicited symptom	All subjects with study vaccine administered	All study visits with study vaccine administered
Concomitant medication	All subjects with study vaccine administered	All study visits with study vaccine administered

For summaries by MedDRA primary preferred term combining solicited and unsolicited adverse events, solicited adverse events will be coded as per the following MedDRA codes.

Solicited symptom	Lower level term code	Corresponding Lower level term decode
Fever	10016558	Fever
Irritability/Fussiness	10022998	Irritability
Diarrhoea	10012727	Diarrhoea
Vomiting	10047700	Vomiting
Loss of appetite	10003028	Appetite lost
Cough/runny nose	10011224	Cough

